As treatments are delivered in a group setting, a random intercept for ‘group’ will be included in all models. The random intercept allows for the responses of individuals within the same group to be correlated with each other. However, in our analyses of pilot data we have found that the variance of the random intercept is often close to zero (indicating little difference between groups). This may be because the treatment protocol is standardised to minimise differences between groups, and outcome largely depends on whether participants complete homework tasks between sessions, which do not overlap with other participants. Some outcomes in the present trial will also be measured after patients have been apart for a long time (i.e., the 1 and 6-month follow ups). The random intercept variance has been so small in analyses of some pilot data that it has caused problems with model convergence. Therefore, if in analyses of trial data, the model with a random intercept for group demonstrates issues with convergence or the random effect has a variance near zero, the random intercept will be removed.

Modelling of Baseline Measurements

Scores collected at baseline could be modelled as a covariate, or as part of the response vector (Mallinckrodt & Lipkovich, 2017). Clinical trial statisticians (e.g., Harrell, 2015; Senn, 2008) often recommend that the baselines be included as a covariate, as this can increase power. Baseline scores may also have a different distribution to responses at other times, which can make joint modelling of the baseline and post-baseline outcomes problematic (Mallinckrodt & Lipkovich, 2017). In the present RCT, baseline score and its interaction with time will be included as a covariate in the fixed effects part of the LMM.

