analyses with outcomes measured at 13 assessments can account for the autocorrelated nature of the residuals without requiring the estimation of as many parameters as would be required with an unstructured matrix. Analyses of pilot data suggest using a heterogeneous CAR1 structure to model the residual errors fits the data better than any of the other correlation structures available in R's nlme package (Pinheiro et al., 2019).

Binary Outcome with 2 Post-Baseline Measurements (SCID-5 Diagnosis)

As all individuals will have a diagnosis of SAD at the baseline assessment, no additional information is gained by including baseline diagnosis in the model. As such, the analysis of change in diagnostic status will only include the diagnoses at the 1-Month and 6-Month follow-ups. To determine whether the proportion of individuals with a SAD diagnosis at the 1-Month and 6-Month follow-ups is significantly different between the treatment groups, a pooled test of the difference in proportions will be carried out.

For each of the imputed datasets, the proportion of individuals in each treatment arm (IE-CBGT & VB-CBGT) with a diagnosis of SAD, and the standard error of that proportion, will be estimated. The difference in proportions, as well as the standard error of that difference, will also be estimated. These estimated proportions and standard errors for each imputed dataset will then be pooled using Rubin's Rules (van Buuren, 2018). These pooled results will give the percentage of individuals in each arm meeting diagnostic criteria at the 1-Month and 6-Month follow-ups, the difference between the arms, confidence intervals for difference, and the significance of the difference.

Ordinal Outcome with 2 Post-Baseline Measurements (Clinician-Rated Severity)

Because clinician-rated severity is an ordinal outcome (rated by category and the categories are ordered in severity) measured on multiple occasions, the analysis will use a cumulative-link mixed-effects model (CLMM) as implemented in the R package 'ordinal' (Christensen, 2019). The CLMM is an extension of the generalised linear mixed-model for use with ordinal data. Baseline severity will be included as a covariate and time will be entered as categorical. A random intercept for each group will be included, but as with the previous analyses will be removed if it shows little variance. To account for the correlation between one- and six-month follow up assessments, a random slope for patient will be used.

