The criteria for having achieved CSC were the same as described in previous pilot research (McEvoy et al., 2015). Individuals were required to have scored above a severity cut-off before treatment, achieved RC, and subsequently scored below the cut-off after treatment. The severity cut-off was defined as the mid-point between the clinical and normative means reported by Carleton et al. (2014), which was 40.56 for the SIAS.

To determine whether the proportions of individuals achieving reliable and/or clinically significant change significantly differed between treatment arms, a pooled test of the difference in proportions was carried out (the same procedure described for the analysis of diagnostic status).

Contrasts for Continuous and Ordinal Outcomes

The primary hypotheses are concerned with whether there are differences between the treatments at one month follow up. In order to determine this, for each continuous and ordinal outcome, the data from all the measurement occasions are jointly modelled using a LMM (rather than say, only using the one-month follow-up data in the analysis; see Mallinckrodt and Lipkovich (2017)). We will then use contrast coefficients to (i) estimate the marginal means for each treatment at each measurement occasion, and (ii) compute the mean difference between treatments and a standard error at the one-month follow up time point. For continuous and ordinal outcomes, we will compute the contrasts using R's emmeans package. For the ordinal outcome this contrast is an odds ratio, representing the difference in probability of belonging to a higher severity rating between the two treatment arms.

Evolution of Outcomes Over Time

A secondary goal of this paper is to understand how differences between the groups evolve over time. Analyses of pilot data suggest these tend to be smaller at post-treatment than at one-month follow up. We have no pilot data for the six-month follow up. Therefore, we will use additional contrasts to examine differences between the treatments at week 12 (end of weekly treatment sessions) and the 6-month follow up. This will provide valuable information about the evolution of treatment outcomes before and after the primary endpoint.

Reporting of Results

Analysis Code and Output

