A key sensitivity analyses will be testing the sensitivity of the results to violations of the missing at random (MAR) assumption. As multiple imputation assumes that the data are MAR, the imputed values could be biased if this is not the case. In other words, if there is a systematic reason for why some individuals did not adhere to treatment, ignoring this when imputing their missing responses could bias the results away from the ‘true’ effect. A common means of testing this assumption is called a ‘tipping-point’ analysis (Mallinckrodt & Lipkovich, 2017). The tipping-point approach to sensitivity analysis is implemented by modifying the imputed data by increasing amounts and identifying the magnitude of changes in imputed data that would be required for the results to no longer be significant (Mallinckrodt & Lipkovich, 2017). This is achieved through the repeated use of what is called a ‘delta-adjustment’ of the imputed values (van Buuren, 2018). A delta-adjustment is simply the addition of a fixed value (delta) to every imputed response. In other words, this approach is

artificially raising or lowering the mean response of all non-adherent individuals. By using increasingly large values of delta (the fixed value), a sensitivity analysis can identify the extent to which the non-adherent individuals would need to differ in their response before there is no longer a significant difference between the treatment groups.

Summary of Confirmatory Analyses

Outcome	Analysis	Fixed Effects	Random Effects	Residual Covariance Structure
SPS & SIAS	Linear Mixed Model	
 • Baseline • Time (Categorical) • Treatment • Baseline*Time • Treatment*Time 	
 • Intercept (Group) 	
 • Unstructured • Heterogenous Variances
BFNES, PROMIS Anxiety & Depression	Linear Mixed Model	
 • Baseline • Time (Piecewise) • Treatment • Baseline*Time • Treatment*Time 	
 • Intercept (Group) 	
 • CAR1 • Heterogenous Variances
Diagnostic Status	Pooled Test of Difference in Proportions	N/A	N/A	N/A
Clinician-Rated Severity	Cumulative-Link Mixed Model	
 • Baseline • Time (Categorical) • Treatment • Baseline*Time • Treatment*Time 	
 • Intercept (Group) • Intercept • Time 	N/A

References

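### The primary SAD-diagnosis test and the RC/CSC test make no allowance for therapy-group clustering, so their CIs and p-values are anti-conservative if the group ICC exceeds zero

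*SAP*

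**What the plan says.** **Diagnosis.** Under Binary Outcome with 2 Post-Baseline Measurements (SCID-5 Diagnosis), the SAP states that "a pooled test of the difference in proportions will be carried out". In each imputed dataset the arm proportions and their standard errors are computed. "The difference in proportions, as well as the standard error of that difference, will also be estimated", and the results are pooled by Rubin's Rules. No group term, cluster-robust standard error or covariate is named. In Summary of Confirmatory Analyses the row for diagnostic status reads "Pooled Test of Difference in Proportions", with fixed effects, random effects and residual covariance all N/A.

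**RC/CSC.** The arm comparison is described as "the same procedure described for the analysis of diagnostic status".

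**Clustering.** Accounting for Nesting Within Group starts from the fact that treatment is given in groups and says that a random intercept for group "will be included in all models". The purpose is explained: "The random intercept allows for the responses of individuals within the same group to be correlated with each other". In pilot data, however, "the variance of the random intercept is often close to zero". The term is to be removed only if the trial data show convergence problems or a variance near zero. The section on clinician-rated severity repeats the inclusion and the removal rule, and the summary table shows a group intercept in every row except diagnostic status.

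**Baseline.** Baseline diagnosis is left out because everyone has SAD at entry, so that "no additional information is gained by including baseline diagnosis in the model". Baseline clinician-rated severity, which is collected and enters the severity model, is not discussed for this outcome.

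**The concern.** The two treatments are different group therapies, so each therapy group belongs to one arm. Positive correlation among patients in the same group then adds directly to the variance of the difference between arms. A standard error that treats patients as independent leaves this out. Rubin's Rules do not put it back: they add variance between imputations, not variance between therapy groups.

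At stake are the confidence interval and p-value of one of three primary hypotheses, and of a secondary outcome. The Multiplicity section plans no adjustment, so nothing else in the plan offsets an inflated error rate. The other two primary outcomes, SIAS and clinician-rated severity, do start with a group term that is tested against the trial data. Diagnosis gets neither the term nor the check, and no reason is given.

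The missing baseline covariate is a different matter. In a randomised comparison it costs precision, not validity.

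**Working it through.** **Inputs.** From the SAP: at least 96 patients in total, 95% confidence intervals, no ICC, no group size, no expected diagnosis rate. There is therefore no SAP figure to reproduce. Assumed: 48 per arm, two-sided 5%, complete data, m = 6, 8 or 12 patients per group, ICC from 0 to 0.10.

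**Step 1: effect of ignoring clustering.** Design effect DE = 1 + (m − 1) × ICC. True SE = naive SE × √DE. Actual type I error = 2 × [1 − Φ(1.96/√DE)].

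Example: m = 8, ICC 0.05 gives DE = 1 + 7 × 0.05 = 1.35, √DE = 1.162, 1.96/1.162 = 1.687, type I error 9.2%.

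| ICC | DE, m = 6 / 8 / 12 | Type I error by formula | By simulation |
|---|---|---|---|
| 0 | 1 / 1 / 1 | 5.0% | 5.2% |
| 0.01 | 1.05 / 1.07 / 1.11 | 5.6 / 5.8 / 6.3% | 5.8 / 6.1 / 6.6% |
| 0.02 | 1.10 / 1.14 / 1.22 | 6.2 / 6.6 / 7.6% | 6.4 / 6.8 / 7.9% |
| 0.05 | 1.25 / 1.35 / 1.55 | 8.0 / 9.2 / 11.5% | 8.4 / 9.6 / 12.0% |
| 0.10 | 1.50 / 1.70 / 2.10 | 11.0 / 13.3 / 17.6% | 11.4 / 13.9 / 18.4% |

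The simulation drew beta-binomial counts (48 per arm, true rate 0.5 in both arms, 200,000 runs) and applied the unpooled two-proportion Wald test.

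**Step 2: what this means for the interval.** At a rate of 0.5 in both arms, naive SE = √(0.25/48 + 0.25/48) = 0.102, so the 95% half-width is 1.96 × 0.102 = 20.0 percentage points. Multiplying by √DE for m = 6 to 12 gives 20.5–21.1 points at ICC 0.01 (×1.025 to ×1.054) and 22.4–24.9 at ICC 0.05 (×1.118 to ×1.245).

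**Step 3: effect of omitting baseline severity.** Simulated with 48 per arm, no clustering and 15,000 runs. The unadjusted difference was compared with a linear-probability ANCOVA with robust SE, at three assumed log-odds slopes per SD of baseline severity. Power is for a treatment log-odds of 1.0.

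| Slope | Null rejection, unadjusted | Mean SE at null, unadjusted → adjusted | Power, unadjusted → adjusted |
|---|---|---|---|
| 0.5 | 5.1% | 0.101 → 0.100 | 61% → 63% |
| 1.0 | 5.2% | 0.101 → 0.094 | 51% → 58% |
| 1.5 | 5.1% | 0.101 → 0.087 | 40% → 52% |

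The unadjusted test keeps its level throughout. The loss is in precision, from negligible to appreciable depending on how prognostic baseline severity is.

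**Step 4: price of a small-sample cluster correction.** With 6 to 10 per group, 96/6 = 16 and 96/10 ≈ 10 groups. Taking df as groups minus 2 gives 14 and 8, with t = 2.14 and 2.31. Against 1.96 these are ratios of 1.09 and 1.18, so the interval is about 9–18% wider even when the ICC is zero.

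**The case against.** **The pilot evidence points to little clustering.** This is the strongest counter-argument. The SAP reports group variance often close to zero and gives plausible reasons: a standardised protocol, individual homework, and patients no longer meeting by follow-up. At ICC 0 to 0.01 the type I error is 5.0–6.3%, which few would worry about. This stands as a limit on the size. It does not dispose of the point: the SAP does not say which pilot outcomes it means, gives no ICC, and did not itself think the pilot data enough to drop the term in advance for the other outcomes.

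**The rule on group intercepts may cover only the linear mixed models.** Confirmatory Longitudinal Analyses first sets diagnosis, clinician-rated severity and RC/CSC apart from the mixed models, then introduces decisions common to those analyses. The N/A entries are open about the absence of a model. A reader might infer a flat contradiction within the SAP; on this reading there is none. But the dependence exists whatever test is used, and the ordinal analysis of severity, also outside the linear mixed models, was given the term.

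**The standard-error formula is not written out.** Correct. That it treats patients as independent is inferred from the method named and the N/A entries.

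**An unadjusted risk difference is a legitimate prespecified measure.** Also correct. Baseline adjustment is an improvement in efficiency, not the repair of an invalid test.

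**Correcting for few clusters costs precision.** True: at ICC 0.01 the 9–18% widening from small df exceeds the 2.5–5.4% by which clustering itself widens the interval.

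**Conclusion.** The point holds conditionally. The primary diagnosis test and the RC/CSC test omit therapy-group clustering with no reason and no check. If the group ICC exceeds zero, the standard error is too small and the CI and p-value are anti-conservative. With 6 to 12 per group, type I error runs from 5.0% (ICC 0) through 5.6–6.3% (0.01), 6.2–7.6% (0.02) and 8.0–11.5% (0.05) to 11.0–17.6% (0.10). Group size, ICC and equal arms are assumptions, and the calculation uses complete data with no imputation variance. The omission is certain; its size is not.

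Three stronger readings are not supported:

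- A reader might infer that the reported p-value will certainly be too small. The SAP's only evidence on clustering suggests that the effect could be negligible.
- A reader might infer that omitting baseline severity adds to the optimism. It does not: null rejection was 5.1–5.2% whatever the prognostic strength. Unadjusted intervals are wider, not narrower.
- A reader might infer that RC/CSC ignores baseline. RC is a change from the pre-treatment score, and CSC requires that score to lie above the cut-off. Only the between-arm test is unadjusted.

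**What to change.** In each imputed dataset, fit a logistic model with treatment and baseline clinician-rated severity, and derive the standardised risk difference, so that the planned effect measure is kept. Allow for therapy group in one of two ways, chosen in the SAP: a cluster-robust standard error with a small-sample correction, or a group random intercept subject to the SAP's existing removal rule. Pool by Rubin's Rules. Do the same for RC and CSC, with the mean baseline SIAS as covariate. Replace the N/A entries for diagnostic status in the summary table, and add a row for RC/CSC, which has none.

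**Cost.** SAP wording and a little more code; no new data. The SAP already cites clubSandwich, but under Model Assumptions and for residual non-normality in the mixed models, so the step from model to standardised risk difference needs its own variance calculation. The statistical price of the cluster-robust route is the 9–18% wider interval at ICC zero with about 10–16 groups. Baseline adjustment offsets part of it: in the simulation above the SE fell by about 1%, 7% or 14% (0.0997, 0.0935 and 0.0871 against 0.101), depending on the assumed slope. The SAP should state this trade-off when it makes the choice.

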In short, the study is a superiority trial that aimed to randomise at least 96 individuals with social anxiety-disorder to one of two 12-week group treatments for SAD (IE-GCBT and VB-GCBT). There is also a one-month follow up group review session. Over 20 outcome measures have been collected at various times before, during, and after treatment. The primary endpoint is the one month follow up (i.e., coinciding with the follow up group review session). This was selected on the basis of pilot data which showed differences between the treatments are larger at one-month follow up than at the end of weekly treatment sessions (McEvoy et al., 2015). No interim analyses or stopping rules were planned, nor have any been used.

The primary hypotheses are that, at the one-month follow up, IE-GCBT will be superior to VB-GCBT in terms of (a) reduction in severity of self-reported social anxiety symptoms (b) percentage of individuals with a SAD diagnosis (c) reduction in clinician-rated severity of social anxiety symptoms. McEvoy et al. (2017) also describe a wide range of additional hypotheses concerning secondary outcome measures, mechanisms of change, and moderation. Given the numerous outcomes and possible research questions, it is not possible to comprehensively report them all in a single paper. Therefore, they will be addressed across several publications.

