We will now describe how each imputed dataset will be analysed. The choice of analytical approach was determined by both the type of measurement of the outcome (e.g., binary or continuous) and the number of repeated assessments (i.e., number times that these outcomes were measured). These attributes for the outcomes are summarised in Table 1. See the trial protocol paper for more information about outcomes in the trial and their measurement properties (McEvoy et al., 2017).

Table 1

Measurement Properties and Repeat Assessments for Outcomes under Analysis

Outcome	Type of Measurement	Number of Measurements	
		Baseline	Post-Baseline
Primary			
SIAS	Continuous	2	5
SCID-5 Diagnostic Status	Binary	1	2
Clinician Rated Severity	Ordinal (Ranges 0 – 8)	1	2
Secondary			
SPS	Continuous	1	5
BFNE-S	Continuous	1	13
FPE	Continuous	1	13
PROMIS Anxiety	Continuous	2	13
PROMIS Depression	Continuous	2	13

All outcomes aside from SCID-5 diagnostic status, clinician-rated severity, and reliable and clinically-significant change will be analysed using Linear Mixed Models (LMM), as implemented in the R package nlme (Pinheiro, Bates, DebRoy, Sarkar, & R Core Team, 2019). There are some aspects of these analyses that will be the same for all outcomes and some that will differ depending on the number of measurement times for each outcome. The analytical decisions that are the same for all outcomes will be described first, followed by separate sections detailing the decisions individual to each analysis. A summary of the analyses and parameterizations of each is presented at the end.

Accounting for Nesting Within Group

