A key concern with the analysis of ordinal data is whether there are sufficient numbers of individuals at each of the rating categories. If there are only a small number of

individuals within a given severity rating, the estimated relationships could be easily influenced by outlying, or simply unrepresentative, responses. This is likely to be the case for the largest and smallest ratings of severity. If severity categories have low numbers of endorsements (< 5), those categories will be collapsed.

It should be noted that the CLMM relies on the assumption of proportional odds. This assumption implies that the effect of the covariates (e.g., treatment) are the same for every category. In other words, regardless of whether the individual has a high or low severity rating, their probability of changing category after receiving treatment is the same. If this is not the case, the resulting estimates of treatment effect are likely to be biased. An alternative is to estimate a different effect for each category. While this is more flexible, and does not assume proportional odds, it also requires estimating more parameters. The analysis of clinician-rated severity will first be carried out assuming proportional odds. The proportional odds assumption will then be evaluated. If there is a substantial departure from proportional odds for a given covariate, the analysis will be refitted with non-proportional odds for that covariate.

Reliable and Clinically Significant Change (SIAS)

Beyond simply testing whether the amount of change in social anxiety symptoms is statistically significant, it is also of interest to examine whether those changes are: a) beyond what would be expected due to measurement error, and b) clinically meaningful. This is the examination of reliable and clinically significant change (RC and CSC, respectively) described by Jacobson and Truax (1991). The analyses will examine the RC and CSC of the SIAS using the multiply-imputed datasets.

The calculation of RC is defined as:

$$RC = \frac{(SIAS_{pos} - SIAS_{pre})}{\sqrt{2 * SE^2}}$$

Where:

$$SE = SD_{pre} * \sqrt{1 - r}$$

Where r is the reliability of the SIAS. For this analysis, the previously described McDonald's Omega coefficient will be used as the estimate of the reliability of the SIAS. If

$RC > 1.96$, this indicates that the amount of change is greater than can be attributed to measurement error.

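### Clinician-rated severity (primary): text and summary table give different patient random effects, and the table's structure leaves the size of the one-month odds ratio barely identified

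*SAP*

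**What the plan says.** Primary hypothesis (c) concerns "c) reduction in clinician-rated severity of social anxiety symptoms" at one month. The SAP's table of measurement properties describes the outcome as "Clinician Rated Severity Ordinal (Ranges 0 – 8) 1 2", that is, one baseline and two post-baseline ratings.

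In the section on the ordinal outcome, "the analysis will use a cumulative-link mixed-effects model (CLMM) as implemented in the R package 'ordinal". There, "Baseline severity will be included as a covariate and time will be entered as categorical", so the modelled responses are the one-month and six-month ratings only. On the patient term the same section says: "To account for the correlation between one- and six-month follow up assessments, a random slope for patient will be used". It mentions no patient intercept.

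The Summary of Confirmatory Analyses lists the random effects of this model as "Intercept (Group) • Intercept • Time". Beside the group intercept, the last two entries can only sensibly be read as a patient intercept and a patient time effect.

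Under Contrasts for Continuous and Ordinal Outcomes, "For the ordinal outcome this contrast is an odds ratio". Standardized Effect Size names the odds ratio as the effect size for ordinal outcomes, and Confidence Intervals promises a 95% interval for the one-month difference. The section on the ordinal outcome gives a removal rule for the group intercept only. Model Convergence says that persistent convergence problems will be met first with more iterations and then with simpler random effects, giving the group intercept as its example.

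**The concern.** The text and the table describe different models for a primary outcome, and each has a problem.

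- **Table (patient intercept plus time).** With two visits this is a fully free 2×2 patient covariance matrix. A cumulative-link model has no residual variance of its own to estimate, because the link sets it. Two ordinal ratings per patient then carry too little information to fix the scale of the latent variable, and the conditional odds ratio is expressed on that scale.
- **Text (a slope, read literally).** If the slope has no intercept beside it and one month is the reference level, the patient effect enters only the six-month rating. The visits then share no patient effect and no correlation is modelled, although modelling it is the purpose given.

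At stake are the published odds ratio and its confidence interval for hypothesis (c).

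**Working it through.** The SAP gives no variance, power or effect figure for this model, so there is none to reproduce.

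**Inputs from the SAP.** At least 96 randomised; two modelled ratings per patient; time categorical; baseline as covariate; an odds ratio as the contrast, which implies a logit link.

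**Assumed inputs.** 96 patients, 5 categories after collapsing, true patient SD 2 on the logit scale, one-month conditional odds ratio 0.40, no group effect, no missing data.

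**1. Count.** Ratings: 96 × 2 = 192. Patient random effects under the table: 96 × 2 = 192, one per rating. The ratio is the same for any number of patients. The three patient parameters are the variance at one month, the variance at six months and their covariance.

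**2. Why the scale floats.** The total latent variance at a visit is s² + π²/3 = s² + 3.29, where s is the patient SD. Ordinal categories show thresholds and effects only relative to the total SD. Two visits therefore inform, in practice, a ratio of spreads and a correlation: two quantities for three parameters. With a probit link the third is exactly unidentified. With a logit link it is identified only through the small difference in shape between logistic and normal.

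Moving s away from 2 rescales everything by about k = √[(s² + 3.29)/(2² + 3.29)], and the odds ratio becomes 0.40^k:

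| s | k | 0.40^k |
|---|---|---|
| 2 | 1.00 | 0.40 |
| 3 | 1.30 | 0.30 |
| 4 | 1.63 | 0.23 |
| 5 | 1.97 | 0.16 |
| 8 | 3.04 | 0.06 |

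**3. Expected likelihood (numerical quadrature, other parameters re-optimised, scaled to 96 patients).** Cost in deviance of fixing the one-month patient SD:

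| SD fixed at | Intercept + time: cost | Odds ratio | Intercept only: cost |
|---|---|---|---|
| 3 | 0.07 | 0.30 | 6.8 |
| 4 | 0.13 | 0.22 | 21 |
| 5 | 0.16 | 0.16 | 38 |

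The odds ratios agree with step 2. The intercept-only model is identified because its latent correlation is s²/(s² + 3.29): 4/7.29 = 0.55 at s = 2 but 25/28.29 = 0.88 at s = 5. The observed agreement between visits therefore pins down s.

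**4. Eight simulated datasets (same assumptions, baseline and its time interaction included).** As the fixed one-month SD rose from 3 to 8, the profile log-likelihood changed by 0.02 to 0.33 (a 95% limit needs 1.92). The odds ratio moved, for example, from 0.25 to 0.044, from 0.16 to 0.013 and, in the mildest case, from 0.66 to 0.39. In 7 of 8 datasets the whole range 2 to 8 stayed within 0.8 log-likelihood units. With a patient intercept only, all eight gave a finite SD (1.68 to 2.74) and odds ratios of 0.23 to 0.73, which is ordinary sampling spread.

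**5. The test.** Likelihood-ratio p-values for treatment at SD 2, 4 and 8, in the three datasets checked:

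| Dataset | p at SD 2 / 4 / 8 | Odds ratio at SD 2 / 4 / 8 |
|---|---|---|
| A | 0.020 / 0.024 / 0.025 | 0.258 / 0.117 / 0.018 |
| B | 0.054 / 0.073 / 0.078 | 0.329 / 0.182 / 0.044 |
| C | 0.040 / 0.047 / 0.048 | 0.292 / 0.142 / 0.026 |

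The odds ratio falls 7- to 14-fold while p changes little.

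**The case against.** **The test survives.** Hypothesis (c) asks whether one arm is superior. The log odds ratio divided by the total latent SD is nearly constant along the ridge: ln 0.40/2.70 = −0.34 at SD 2 and ln 0.16/5.32 = −0.34 at SD 5. This stands, and it limits the point to the size of the odds ratio and its interval. A reader might infer that the model cannot be fitted or that the result is arbitrary. That goes too far: under a logit link the parameters are weakly identified rather than inestimable.

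**The slope sentence may be shorthand.** The SAP states no time coding. A patient-by-visit term without an intercept could mean one correlated effect per visit, and the table suggests intercept plus time. So the SAP does not establish that the text models no correlation; that holds only for the literal reading with one month as reference. The wording still needs reconciling, and the more natural reading leads to the weakly identified model.

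**A fallback exists.** Model Convergence allows simpler random effects, and the group intercept is only an example there. But the rule needs a reported convergence problem, which a flat likelihood need not produce, and it names no patient term for removal.

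**Pooling.** A reader might infer that 100 imputed fits stopping at different points on the ridge would spoil the pooled interval. This is plausible, but no imputation or pooling was run, so it is not established.

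**Proportional odds.** A reader might also infer that the rule that "the analysis will be refitted with non-proportional odds for that covariate" leaves hypothesis (c) without a single odds ratio. The SAP does not support that: it fits the proportional-odds model first and gives its reason for refitting. That is a separate trade-off.

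**Simulation truth.** The data were generated with a patient intercept only, so the remedy was tested only where it is correctly specified. That is fair. The ridge itself follows from one random effect per rating and a fixed residual variance, not from the chosen values.

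**Conclusion.** The point holds and should be fixed. The text and the summary table disagree on the patient random effects of a primary outcome. Under the table's structure the effect size is so weakly identified that, with the assumed inputs, the odds ratio runs from 0.40 to 0.16 for less than 0.2 deviance units. The exact figures depend on the assumed category number, patient SD and odds ratio; the flatness comes from the structure. The evidence does not show that the superiority test is invalid: direction and p-value were fairly stable, though only three datasets were checked for this. What is unreliable is the reported odds ratio and its confidence interval.

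**What to change.** In both the section on the ordinal outcome and the Summary of Confirmatory Analyses, specify one random intercept for patient plus the therapy-group intercept, with time as a categorical fixed effect and no patient-level time effect. Label the patient term as such in the table, where the entries beside the group intercept do not name their unit.

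This is a wording change to a plan written before the data were made available. The small downside is that one patient variance is shared by the one-month and six-month ratings, so a real difference in patient spread between visits would not be modelled. In return, the model represents the correlation that the text sets out to capture, and the odds ratio sits on a scale that two ratings per patient can estimate.
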